2.2 Protocol Deviations

The following general categories will be considered important protocol deviations (IPDs) and will be listed and discussed in the CSR as appropriate:

- Inclusion criteria deviations: Patients who deviate from inclusion criteria 2, 6, 11 and/or 13 per Section 5.1 of the CSP.
- Exclusion criteria deviations: Patients who deviate from exclusion criteria 4 and/or 13 per Section 5.2 of the CSP.
- Discontinuation criteria for study product met but patient not withdrawn from study treatment.
- Investigational product (IP) deviation:
 - (a) Patient received incorrect IP to that to which they were randomized.
 - (b) Patients who were randomized but did not receive IP.
- Excluded medications taken: Received prohibited concomitant systemic anti-cancer therapy.
- Deviations related to study procedure: Baseline RECIST scan > 49 days before randomization.

Patients who receive the wrong treatment at any time will be included in the safety analysis set as described in Section 2.1. During the study, decisions on how to handle errors in treatment dispensing (with regard to continuation/discontinuation of study treatment or, if applicable, analytically) will be made on an individual basis with written instruction from the study team leader and/or statistician.

The IPDs will be listed and summarized by randomized treatment group. IP deviation of patients who were randomized but did not receive IP will lead to exclusion from the safety analysis set. None of the other deviations will lead to patients being excluded from the analysis sets described in Section 2.1. A per-protocol analysis excluding patients with specific IPDs is not planned.

The programmatic determination of the IPDs above will be a separate process outlined in the study Protocol Deviations Plan, which will also include full details regarding IPDs as well as the activities and responsibilities related to the IPD process.

In addition, other study deviations captured from the eCRF module for inclusion/exclusion criteria will be tabulated and listed. Any other deviations from monitoring notes or reports may be reported in an appendix to the CSR.

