3. PRIMARY AND SECONDARY VARIABLES

3.1 Derivation of RECIST Visit Responses

For this adjuvant study, where patients with no evidence of disease at baseline (as assessed by CT/magnetic resonance imaging [MRI]) will be entered in the study, the definition of new lesions (NLs) in RECIST 1.1 is used for the assessment of disease recurrence.

For all patients, the RECIST tumour response data will be used to determine each patient's visit response according to RECIST version 1.1. It will also be used to determine if and when a patient has progressed in accordance with RECIST.

Baseline radiological tumour assessments are to be performed no more than 28 days + 7 days prior to randomization and ideally as close as possible to the date of randomization. Tumour assessments are then performed every 8 weeks \pm 1 week following randomization until week 48, and then every 12 weeks \pm 1 week until unequivocal disease recurrence or primary DFS analysis. Upon detection of disease recurrence, an additional follow-up scan should be performed 4 to 8 weeks later and evaluated using post-progression radiological criteria.

If an unscheduled assessment is performed, and the patient has not had disease recurrence, every attempt should be made to perform the subsequent assessments according to the original

imaging visit schedule (relative to the date of randomization). If a dose delay of study treatment (i.e. durvalumab/placebo) occurs, RECIST scans should continue according to the original imaging visit schedule. This schedule is to be followed in order to minimise any unintentional bias caused by some patients being assessed at a different frequency than other patients.

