3.2 Efficacy Variables

3.2.1 Disease-Free Survival (DFS)

Disease-free survival as assessed by the Investigator is the primary endpoint in this study and is defined as the time from the date of randomization until any one of the following events below, whichever occurs first, regardless of whether the patient withdraws from randomized therapy or receives another anti-cancer therapy prior to disease recurrence (i.e., date of DFS event or censoring – date of randomization + 1 day):

- Date of disease recurrence using Investigator assessments according to RECIST 1.1
 - Local, regional, or distant disease recurrence
 - Diagnosis of a second primary NSCLC
- Date of death from any cause

Disease recurrence should be based on the finding of an unequivocal NL. However, if a NL is initially equivocal (i.e. where an equivocal lesion converts to unequivocal), then the progression date should be backdated to the post-baseline follow-up scan when the NL first appeared without an intervening period of lesion absence. If equivocal lesions are present at baseline, they will not be documented on the baseline eCRF.

Patients who have not experienced disease recurrence and are alive at the time of DCO will be censored at the latest date of assessment from their last evaluable RECIST 1.1 assessment.

However, if the patient experiences disease recurrence or dies after 2 or more missed visits, the patient will be censored at the latest evaluable RECIST 1.1 assessment prior to the 2 missed visits (note: an NE visit is not considered a missed visit). Given the scheduled visit assessment scheme (i.e. every 8 weeks \pm 1 week after randomization for the first 48 weeks, then every 12 weeks \pm 1 week thereafter until appearance of disease recurrence or until

primary DFS analysis) the definition of 2 missed visits will change. The definitions are shown in [Table 3](#).

Table 3 Definition of Two Missed Visits

Previous RECIST assessment	Two missed visits (duration)	Explanation
Study day < 274 (week 39)	18 weeks	$2 \times 8 \text{ weeks} + 1 \text{ week for an early assessment} + 1 \text{ week for a late assessment} = 18 \text{ weeks.}$
Study day 274 to < 344 (>week 39 to < week 49)	22 weeks	Over this period, the scheduled frequency of RECIST assessments changes from q8w to q12w. Take the average of 8 and 12 weeks which gives 10 weeks. $2 \times 10 \text{ weeks} + 1 \text{ week for an early assessment} + 1 \text{ week for a late assessment} = 22 \text{ weeks.}$

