Study day 344 onwards (week 49)	26 weeks	$2 \times 12 \text{ weeks} + 1 \text{ week for an early assessment} + 1 \text{ week for a late assessment} = 26 \text{ weeks.}$

RECIST Response Evaluation Criteria in Solid Tumours; q8w Every 8 weeks; q12w Every 12 weeks.

If the patient has no evaluable assessments or does not have baseline data, they will be censored at day 1 unless they die within 2 visits of baseline (i.e. 17 weeks [$2 \times 8 \text{ weeks} + 1 \text{ week for a late assessment}$]), then they will be treated as an event with the date of death as the event date. Additionally, patients with unequivocal evidence of disease at baseline (as assessed by the Investigator) will be censored at randomization (day 1).

The primary endpoint analysis of DFS on the FAS analysis set will be based on Investigator assessments according to RECIST 1.1. The DFS time will always be derived based on scan/assessment dates and not visit dates.

RECIST 1.1 assessments/scans contributing toward a particular visit may be performed on different dates. The following rules will be applied:

- For Investigator assessments, the date of disease recurrence will be determined based on the earliest of the RECIST assessment/scan dates of the component that indicates disease recurrence.
- When censoring a patient for DFS, the patient will be censored at the latest of the scan dates contributing to a particular overall visit assessment.

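### SAP Table 3 does not say where the two-missed-visit clock starts, or where to censor, when the previous scan is baseline; counted from the scan date, one missed scan can count as two

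*SAP*

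**What the plan says.** SAP 3.2.1 gives the trigger as a count of visits: it applies "if the patient experiences disease recurrence or dies after 2 or more missed visits". In that case "the patient will be censored at the latest evaluable RECIST 1.1 assessment prior to the 2 missed visits". The same section then refers to Table 3 for what two missed visits means.

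Table 3 is keyed to the timing of the previous RECIST assessment. Its first row begins "Study day < 274 (week 39" and sets 18 weeks, built from two 8-week intervals plus one week for an early and one week for a late scan. The row has no lower bound, and no row is set aside for baseline.

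Three other places bear on the point:

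- SAP 3.1 allows the baseline scan "no more than 28 days + 7 days prior to randomization", which is 35 days, and schedules later scans every 8 weeks from randomization, each with a one-week tolerance.
- SAP 2.2 refers to this scan as a RECIST scan and makes it an important deviation only at "Baseline RECIST scan > 49 days before randomization".
- The paragraph after Table 3 covers patients with no evaluable assessments or no baseline data, who are "censored at day 1 unless they die within 2 visits of baseline (i.e. 17 weeks". Here the allowance is two 8-week intervals plus one late week, with no early week. It does not say whether baseline means the scan date or Day 1.

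**The concern.** The 18-week limit makes sense only if the previous scan fell within a week of its scheduled date. The baseline scan has no such scheduled date and can float over five weeks before randomization. A programmer who applies Table 3 as written would take the baseline scan as the previous assessment, because its study day is below 274, and would count from its date. SAP 3.2.1 supports that choice by basing DFS on scan dates rather than visit dates, and SAP 4.1.1 by defining efficacy baseline as the last measurement before randomization. The table could then treat one missed scan as two, against the section's own count of visits.

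The patients exposed are those who miss the first follow-up scan and recur or die soon after. Dropping those events removes early failures, so the loss is informative and makes DFS look better in the arm where it occurs. Under SAP 4.2.2.1 the main DFS results are event and censoring counts and Kaplan-Meier curves, and no alternative censoring rule is planned that would show the effect.

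**Working it through.** **Inputs**

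- Table 3 limits and study-day cut-points: SAP 3.2.1.
- Baseline lead *b*, 0 to 35 days before randomization: SAP 3.1.
- Follow-up scans at Week 8, Week 16 and so on from randomization, each plus or minus one week: SAP 3.1.
- DFS time = event or censoring date − randomization date + 1: SAP 3.2.1.
- About 30 patients randomized 1:1: SAP 1.2.

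**The plan's own figures**

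- Row 1: 2×8 + 1 + 1 = 18 weeks (126 days). Row 2: 2×10 + 1 + 1 = 22 weeks. Row 3: 2×12 + 1 + 1 = 26 weeks.
- Death rule: 2×8 + 1 = 17 weeks (119 days).
- Cut-points: (274 − 1)/7 = week 39; (344 − 1)/7 = week 49.

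All agree with the SAP.

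**Where 18 weeks fits.** Between two post-baseline scans with one missed, the longest in-window gap is an early Week 8 scan (Week 7) to a late Week 24 scan (Week 25): 25 − 7 = 18 weeks. That reaches the limit without passing it, so I read the rule as more than 18 weeks.

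**Where it does not fit.** Take the baseline scan as the previous assessment, with only Week 8 missed and recurrence on the next scan at week *w*. The gap is 7*w* + *b* days, against 126.

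| Lead *b* (days) | Scan at Week 15 | Scan at Week 16 | Scan at Week 17 |
|---|---|---|---|
| 0 | 105 | 112 | 119 |
| 7 | 112 | 119 | 126 |
| 14 | 119 | 126 | **133** |
| 21 | 126 | **133** | **140** |
| 28 | **133** | **140** | **147** |
| 35 | **140** | **147** | **154** |

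Bold entries exceed 126 days. The limit is passed when *b* > 126 − 7*w*: over 21 days for a Week 15 scan, over 14 for Week 16, over 7 for Week 17. At the permitted maximum lead the gap is 147/7 = 21 weeks, or 154/7 = 22 weeks with a late scan.

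**Resulting censoring time.** The rule censors at the last evaluable assessment before the gap, here the baseline scan. At *b* = 35 the DFS time is −35 + 1 = −34 days. Day 1 censoring is written only for patients with no evaluable assessments, no baseline data, or unequivocal disease at baseline. A patient whose Week 16 scan shows recurrence is in none of these groups.

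**Death rule.** Counted from a scan 35 days before randomization, 17 weeks ends 119 − 35 = 84 days (Week 12) after randomization. Only Week 8 has fallen due by then; the Week 16 window opens at Week 15.

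**Clock from randomization instead.** A Week 16 scan is at 112 elapsed days and the latest in-window one at 119, so neither is more than 119 and the recurrence stays an event. If Weeks 8 and 16 are both missed, the earliest in-window Week 24 scan is at 23×7 = 161 days, which is over 119 and is still censored as intended.

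**Size.** 30/2 = 15 per arm; 1/15 = 6.7 percentage points of an arm's event proportion.

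**The case against.** The best reply is that the SAP never says that the clock starts at the baseline scan. The trigger is a count, as it is in Protocol 9.4.1.2, and missing Week 8 alone is one visit. Table 3 is introduced by a schedule that runs from randomization, and the 17-week death rule leaves out the early-scan week, which suits a fixed origin such as Day 1. SAP section 6 declares no change to this rule. A negative DFS time also suggests that the literal reading was not intended.

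This reply stands as to intent. A reader might infer that Table 3 definitely starts the clock at the scan, or that the event is censored at Day 1; the documents support neither. The reply does not remove the defect, because the SAP makes Table 3 the definition of the count, and no line says to count from randomization.

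A second reply is that long leads should be uncommon: SAP 3.1 asks for scans close to randomization, and Protocol 4.1 asks sites to schedule scans within two weeks of each plasma draw. That is fair, but the protocol also lets surveillance or post-therapy scans serve as baseline within 28 plus or minus 7 days (Table 1 and Table 2 footnotes), so leads over 14 days remain foreseeable.

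Third, the analysis is exploratory, and all RECIST data and the reasons for censoring are reported, so an affected patient could be found by hand. That limits the harm but does not settle the rule.

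**Conclusion.** The point holds as a gap in the definition with a conditional consequence. Table 3 gives neither the clock start nor a usable censoring date when baseline is the previous assessment. Read literally, it can treat one missed scan as two when the baseline lead exceeds 14 days (7 to 21 depending on scan timing). The 17-week death rule leaves its origin equally open.

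The number of affected patients cannot be derived, since no rate of missed Week 8 scans and no distribution of baseline leads is given; it may be none. If the lead were uniform over 0 to 35 days (my assumption), 21/35 = 60% of Week 16 recurrences after a missed Week 8 scan would be lost, with a range of 14/35 = 40% to 28/35 = 80% for scans a week early to a week late. A reader might take that as the share of all early events, or infer bias between arms. Neither follows: it applies only to that subgroup, and nothing shows which arm would be affected. What can be said is that one reclassified event moves an arm's event proportion by about 6.7 points. This is worth correcting in a descriptive analysis of about 30 patients, but it does not threaten a formal test, because none is planned.

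**What to change.** 1. Add a row to Table 3: *Previous RECIST assessment = baseline: two missed visits if more than 17 weeks (119 elapsed days) after the date of randomization.* Elapsed days need to be specified because DFS time adds one day: a late in-window Week 16 scan is 119 elapsed days but study day 120, and a limit of study day 119 would still censor it.
2. State that patients meeting this row are censored at Day 1, so that no negative time arises.
3. Count the 17-week death rule in the following paragraph from the date of randomization as well.

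The cost is one table row and two short statements in the SAP, with a matching change in the derivation program. All dates needed are already collected.

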Optional Gx sample (DNA element for long-term storage/future use) s		X							8.6.2	
Efficacy evaluations										
Disease assessments (RECIST 1.1)	X t	Disease assessments occur q8w ± 1w until Week 48, then q12w ± 1w (relative to the date of randomization) until appearance of RECIST 1.1-defined disease recurrence or completion of the study. u,v,w							8.1 Appendix G	
Tumor biopsy (optional) xy		Upon detection of RECIST 1.1-defined disease recurrence, an additional follow-up CT scan should be performed 4-8w later x and evaluated using post-progression radiological criteria.  At recurrence							8.7.2.2	

a In order to minimize the time an MRD+ patient is in second screening (ie, the time from receiving an MRD+ result to being randomized and starting treatment), a patient may sign ICF2a as soon as MRD+ test results are received. In addition, the Investigator should proactively schedule CT and/or MRI scans of the chest/abdomen and brain to coincide within the weeks following q6w plasma collection visits that are not aligned with the q12w CT scan schedule (ie, Week 6, 18, 30, etc, relative to the start of surveillance). A CT or MRI scan of the brain should also be proactively scheduled to occur within the week following the q12w CT scan.

- b Every effort should be made to minimize the time between randomization and starting treatment (ie, within 3 days of randomization).
- c Written informed consent and any locally required privacy act document authorization must be obtained prior to performing any protocol-specific procedures. The procedures outlined in this table will be initiated with the signing of ICF2a.
- d Body weight is recorded at each visit along with vital signs.
- e Any clinically significant abnormalities detected require triplicate ECG results.
- f Collected prior to dosing of each cycle and as clinically indicated. Serum or plasma clinical chemistry (including LFT monitoring) and hematology and urinalysis, may be performed more frequently if clinically indicated. If screening clinical chemistry and hematology assessments are performed within 3 days prior to Day 1 (first infusion day), they do not need to be repeated at Day 1.
- g Free T3 or free T4 will only be measured if TSH is abnormal or if there is clinical suspicion of an AE related to the endocrine system.

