## 9.2 Sample size determination

Approximately 284 patients with stage II-III NSCLC who are MRD+ will be randomized 1:1 to durvalumab or placebo. Of the patients randomized into the study, at least 170 patients are required to be PD-L1 TC $\geq$ 1% at study entry. The primary analysis is planned to be performed in the PD-L1 TC $\geq$ 1% analysis set. An analysis on the FAS (all MRD+ stage II-III NSCLC patients randomized) will be performed as a secondary objective of the study. Randomization will be stratified by PD-L1 status (TC<1% vs TC $\geq$ 1%), time from the start of surveillance to the emergence of MRD ( $\leq$ 6 months vs >6 months), and prior neoadjuvant immunotherapy (Yes vs No). In this study, the start of surveillance is defined as the day the plasma sample used to determine a patient's MRD status post-curative intent therapy is collected.

The study is sized for the primary endpoint of DFS in the PD-L1 TC $\geq$ 1% analysis set and for the secondary endpoint of DFS in the FAS.

The analysis of the primary endpoint (DFS) will occur when approximately 118 DFS events have occurred (69% maturity) in the PD-L1 TC $\geq$ 1% analysis set. If the true DFS HR is 0.55 in the PD-L1 TC $\geq$ 1% analysis set, the study will provide at least 90% power to demonstrate a statistically significant difference for DFS with overall 2-sided significance level of 5%; this translates to 3.2-month benefit in median DFS over 4 months on placebo, or 8.4% difference in 2-year DFS rate over 1.5% on placebo, if DFS is exponentially distributed. The smallest treatment difference that would be statistically significant is an HR of 0.7.

The study is also sized to provide at least 90% power for the DFS endpoint in the FAS. The analysis will be performed at the same time as the primary analysis, when it is expected that approximately 197 DFS events have occurred (69% maturity) in the FAS. If the true DFS HR is 0.63 in this population, this will provide at least 90% power to demonstrate a statistically significant difference for DFS, assuming overall 5% 2-sided

significance level; this translates to a 2.3-month benefit in median DFS over 4 months on placebo, or 5.6% difference in 2-year DFS rate over 1.5% on placebo, if DFS is exponentially distributed. The smallest treatment difference that would be statistically significant is an HR of 0.76.

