#### **9.4.1.2 Primary endpoint: disease-free survival**

DFS is defined as the time from the date of randomization until the date of disease recurrence (local, regional, or distant disease recurrence or second primary NSCLC) using Investigator assessments according to RECIST 1.1, or date of death due to any cause, whichever occurs first.

Patients who are disease-free, ie, have not experienced disease recurrence, and alive at the time of analysis will be censored at the latest date of assessment from their last evaluable RECIST 1.1 assessment. However, if the patient experiences disease recurrence or dies after 2 or more missed visits, the patient will be censored at the latest evaluable RECIST 1.1 assessment prior to the 2 missed visits. If the patient has no evaluable assessments or does not have baseline data, they will be censored at Day 1 unless they die within 2 visits of baseline, then they will be treated as an event with the date of death as the event date. The primary endpoint analysis of DFS will be based on Investigator RECIST 1.1 assessments.

The DFS time will always be based on scan/assessment dates and not visit dates.

DFS rate at 6 and 12 months is defined as the proportion of patients alive and disease-free at 6 and 12 months respectively, estimated from Kaplan-Meier plots of the primary endpoint of DFS.

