Considering the approval of neoadjuvant and adjuvant immunotherapy options for patients with resectable Stage II-III NSCLC, AstraZeneca has decided to close enrollment early to

MERMAID-2 (D910MC00001). A total of 416 patients have signed informed consent for the study. This section describes the procedures required for all patients enrolled in the study and ensures that eligible patients have access to open-label durvalumab where appropriate (see Section 10.2 for details). At the time of implementation of CSP v2.0 at site, durvalumab will be supplied to sites for patients eligible to start open-label treatment. Study assessments will cease (except for serious adverse event identification and reporting and pregnancy reporting) and patients will continue with standard of care safety and efficacy assessments (based on local clinical practice).

[figure not shown]

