1.2 Study Design

This is a Phase III, randomized, multicenter, double-blind, placebo-controlled study to evaluate the efficacy and safety of durvalumab adjuvant therapy compared to placebo in patients with stage II-III non-small cell lung cancer (NSCLC) who have undergone curative intent therapy (complete resection ± neoadjuvant and/or adjuvant therapy), who have no evidence of RECIST 1.1- defined disease recurrence, and who become minimal residual disease-positive (MRD+) during a 96-week surveillance period.

Prior to CSP V2.0, the study was designed to screen approximately CCI patients and randomize approximately CCI MRD+ patients with stage II-III NSCLC whose tumors are epidermal growth factor receptor (EGFR) and anaplastic lymphoma kinase (ALK) wild type,

and who have completed curative intent therapy. Randomized patients were to include approximately **CC1** PD-L1 TC \geq 1% and **CC1** PD-L1 TC<1% patients.

Following the decision to close recruitment early, a total of 416 patients have signed informed consent for the study and approximately 30 are expected to be randomized within the study.

Eligible patients will be enrolled in a 96-week surveillance period during which they will be monitored for the emergence of MRD. During surveillance, the patient will be evaluated for MRD by plasma sampling every 6 weeks (q6w \pm 3d) and will receive computed tomography (CT) scans every 12 weeks (q12w \pm 1w) for up to 96 weeks.

Patients who become MRD+ during surveillance (including cases where analysis of the first plasma sample collected [marking the start of surveillance] returns an MRD+ status) will undergo a second screening period. Note: Patients who received prior neoadjuvant immunotherapy must be MRD- based on analysis of the first plasma sample collected (which marks the start of surveillance).

MRD+ patients will be randomized 1:1 to treatment with durvalumab monotherapy 1500 mg or placebo every 4 weeks (q4w) intravenously (IV). Randomization will be stratified by PD-L1 status (TC<1% vs TC \geq 1%), time from start of surveillance to emergence of MRD (\leq 6 months vs >6 months), and prior neoadjuvant immunotherapy (Yes vs No).

[figure not shown]
Patients will be treated for up to a total of 24 months (26 cycles), until disease recurrence, or until other specific treatment discontinuation criteria are met (whichever comes first).

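### SAP Table 3 gives a Week-48 scan a 22-week limit when its next two intervals are both 12 weeks, so a Week-72 recurrence after one missed scan is censored as two missed visits (low impact)

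*SAP*

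**What the plan says.** Protocol section 9.4.1.2 sets the primary-endpoint rule: "if the patient experiences disease recurrence or dies after 2 or more missed visits, the patient will be censored", with the censoring date at the last evaluable scan before the gap. It gives no durations. SAP section 3.2.1 repeats the rule and defines two missed visits in Table 3, by the study day of the previous scan:

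- before day 274: 18 weeks, from two 8-week intervals plus one week early and one week late;
- "Study day 274 to < 344 (>week 39 to < week 49"): 22 weeks, from the average of an 8-week and a 12-week interval, because the scan frequency changes over this period;
- "Study day 344 onwards (week 49"): 26 weeks, from two 12-week intervals plus two weeks.

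The scan schedule is the same in both documents. SAP section 3.1 has 8-weekly scans "following randomization until week 48, and then every 12 weeks". The disease-assessment row of protocol Table 2 reads "Disease assessments occur q8w ± 1w until Week 48, then q12w ± 1w (relative to the date of randomization").

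**The concern.** The two cut points are not placed in the same way. Day 274 is the earliest in-window day for the Week-40 scan. Day 344 is the latest in-window day for the Week-48 scan. The 22-week row therefore holds two scheduled scans with different futures. After Week 40 the next intervals are 8 and 12 weeks, as the table explains. After Week 48 no 8-week interval remains.

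For a Week-48 scan the limit is four weeks too short, and one missed scan is read as two. A real DFS event then becomes a censored observation at Week 48. DFS in the full analysis set is the primary endpoint, reported as event and censoring counts with reasons and as Kaplan-Meier curves (SAP section 4.2.2.1). In so small a trial, one relabelled patient would be visible.

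**Working it through.** **Inputs.** Scans at Weeks 8, 16, 24, 32, 40, 48, 60, 72, 84 and so on, each ±7 days. Study day = 7 × week + 1 (SAP section 3.2.1 counts randomization as day 1). Limits: 18, 22 and 26 weeks = 126, 154 and 182 days.

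**Reproducing the table.** 2×8+2 = 18; 2×10+2 = 22; 2×12+2 = 26. Week 39 is day 274 and Week 49 is day 344. All stated figures reproduce.

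**Next two intervals plus two weeks, by last scan:**

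| Last scan (day) | Next two scans | Weeks needed | Weeks applied |
|---|---|---|---|
| Week 32 (225) | 40, 48 | 8+8+2 = 18 | 18 |
| Week 40 (281) | 48, 60 | 8+12+2 = 22 | 22 |
| Week 48 (337) | 60, 72 | 12+12+2 = 26 | **22** |
| Week 60 (421) | 72, 84 | 12+12+2 = 26 | 26 |

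**The affected patient.** Last scan Week 48 (day 337), Week 60 missed, recurrence at Week 72 (day 505): the gap is 505 − 337 = 168 days. That exceeds 154, so the patient is censored. It is below 182, so the next row would count an event.

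**Not a window-edge effect.** The Week-48 window is days 330 to 344, and days 330 to 343 fall in the 22-week row. The smallest possible gap from that row to the Week-72 window (days 498 to 512) is 498 − 343 = 155 days, still over 154. So all 14 × 15 = 210 date pairs with the last scan on days 330 to 343 are misclassified, out of 15 × 15 = 225 for Week 48. Only day 344 escapes. For every other last scan from Week 8 to Week 72 the count is 0 of 225. These counts check the logic; they are not a frequency of harm.

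**Deaths.** After a day-337 scan with only Week 60 missed, a death from day 492 (337 + 155) to day 512, the end of the Week-72 window, is also censored: 21 days.

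**Expected number, assuming full follow-up.** SAP section 1.2 says "approximately 30 are expected to be randomized within the study"; I assume 15 per arm. Protocol section 9.2 plans exponential DFS, with a "2.3-month benefit in median DFS over 4 months on placebo" in the full analysis set (HR 0.63) and an HR of 0.55 in the PD-L1 TC≥1% set. The durvalumab medians are 4/0.63 = 6.35 and 4/0.55 = 7.27 months. With S(t) = exp(−ln2 × t/median), Week 48 at 11.04 months and Week 72 at 16.56 months:

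- S at Week 48: 0.148 placebo; 0.300 or 0.349 durvalumab. Disease-free: 15 × (0.148 + 0.300) = 6.7, or 15 × (0.148 + 0.349) = 7.5.
- S at Week 72: 0.057 placebo; 0.164 or 0.206 durvalumab.
- Events between: 15 × (0.091 + 0.136) = 3.4, or 15 × (0.091 + 0.143) = 3.5.
- If 3% to 10% (assumed) miss Week 60 alone: 0.03 × 3.40 = 0.10 to 0.10 × 3.51 = 0.35 patients.

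**Early closure.** Under protocol section 10.1, "Study assessments will cease (except for serious adverse event identification and reporting and pregnancy reporting") once protocol v2.0 is implemented at a site; those dates are not given. Week 72 is 504 days after randomization. Reaching it by 2 August 2022, the amendment date, requires randomization by 16 March 2021. Reaching it by 31 December 2022 (assumed) requires randomization by 14 August 2021.

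**The case against.** The arithmetic is not in dispute; the weight given to it is.

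Table 3 can be read as the operative definition, with 22 weeks a deliberate average over a transition. The next-two-intervals formula is then my reconstruction. It is true that the protocol gives no durations. But the formula returns all three stated values, and the row's explanation is the move from 8-weekly to 12-weekly scans, which is complete at Week 48. SAP section 6 lists no departure from the protocol's two-visit rule.

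The 0.10 to 0.35 figure is an upper-end estimate, and that objection stands. It assumes full follow-up. It also treats every event between Weeks 48 and 72 as surfacing late enough to breach 154 days. Unscheduled evaluable scans reset the clock, and a non-evaluable visit is not a missed one. SAP section 5.2 dates the first IDMC meeting to 21 November 2022, with a trigger of about 12 months after first dose or about 50 dosed patients. If the 12-month trigger governed and the data cut fell within six months before that meeting, the first patient would reach Week 72 between about October 2022 and April 2023. Few patients, if any, would then have a protocol Week-72 scan.

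The listings of all RECIST data would also let a reader find an affected patient. That limits the harm but does not correct the derived endpoint.

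**Conclusion.** The concern holds. As written, the primary-endpoint derivation censors after one missed visit when the last scan is on days 330 to 343, which includes the on-time Week-48 scan. This conflicts with the two-visit rule in SAP section 3.2.1 and protocol section 9.4.1.2. That conclusion needs only the scan schedule and Table 3.

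The practical impact is low: most likely 0 patients, possibly 1. The size rests on about 30 randomized patients, the protocol's planning assumptions for DFS, an assumed 3% to 10% rate of missing Week 60 alone, and unknown site implementation dates. The rule is the same in both arms and the analysis is descriptive, so no treatment-effect bias is claimed.

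**What to change.** In SAP Table 3, change row 2 to study day 274 to <330 (week 39 to <week 47) and row 3 to study day 330 onwards (week 47), and change the code to match. Both cuts then sit on the early edge of a visit window.

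With the cut at day 330, the largest gap after one missed visit from Week 48 is 512 − 330 = 182 days, which does not exceed 182. One missed visit is flagged in 0 of 225 date pairs, and two missed visits in 225 of 225, for every last scan from Week 8 to Week 72. No other scheduled scan changes row.

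The cost is two table cells and one code change. Because SAP v2.0 is already approved, it also needs a short amendment or a documented change in the CSR.

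A separate point does not affect this result. Protocol section 7.1.1 and footnote m of protocol Table 3 give 12-weekly scans after treatment stops, while the Table 3 row and sections 8.1 and 8.1.1 keep 8-weekly scans to Week 48. Sections 7.1.1 and 8.1 are marked not applicable after v2.0, but the passages need reconciling if they are used to decide which past scans were due.
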